3.1 Methods

This will be a pilot, 12-month phase II, open label, randomized, two-arm, single-blinded, placebocontrolled, parallel clinical trial of individuals undergoing TPAIT. The two study arms consist of HCQtreated and placebo-treated individuals. To take into consideration an expected more favorable outcome in beta cell function when higher IEQ/Kg body weight is infused, MMTT and C-peptide measurement prior to surgery will be used to assign potential subjects to either a predicted lower or higher IEQ/Kg group. This "distinguo" will be useful in the analysis of the results. Subjects from each group will be evenly distributed and randomized into the two treatment arms.

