3.2 Sample

All patients undergoing TPIAT for CP in the Cleveland Clinic Foundation (CCF) will be under the auto islet registry (Institutional Review Board (IRB) number 08-340) and are potential candidates for the study.

A total of **10 patients** scheduled for TPAIT at CCF, who meet the inclusion/exclusion criteria for TPAIT, confirmed by a multidisciplinary team, consisting of a hepatobiliary surgeon, gastroenterologist, endocrinologist, diabetes educator, social worker, nutrition therapist, psychologist, and pain management team will be recruited into the study. The inclusion/exclusion criteria for entry into the trial, which consists of two parts (criteria for TPAIT and then criteria to be enrolled into this pilot trial), are summarized in Table 1. Historically, gender representation has been equal in the cohort of patients undergoing TPAIT at CCF [1]. Although a trend to better outcome in females was observed even though the mechanisms are unknown [1], the most significant predictor of metabolic function in patients

undergoing TPAIT is the islet mass infused, which will be factored into this trial in two ways: 1) by pretesting and assigning patients to predicted islet yield groups as has been described previously and 2) by normalizing parameters of metabolic function per IEQ/Kg infused.

Arm 1 (n=5) subjects will receive a pre-transplant 200 mg daily dose of HCQ 30 days before TPAIT and will continue on the drug for 3 months after surgery. This dosage will not exceed a daily dose of 5 mg/kg/day using actual body weight due to potential risk of retinal toxicity; patients weighing less than 40 kg will be excluded from study.

Arm 2 (n=5) subjects will receive placebo treatment following the same schedule as in Arm 1.

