3.5 Benefits and risks

Hydroxychloroquine is considered to be among the safest antirheumatic medications with the potential for any serious adverse event being extremely rare [53]. Gastrointestinal symptoms are the most common side effects, nausea being the most common. The relative safety of HCQ has resulted in no regular laboratory testing required to monitor for toxicities. Monitoring for adverse events is clinical. Retinopathy is the most notable complication of HCQ, though any serious ophthalmologic toxicity is rarely seen with regular follow up. The risk of retinopathy increases with higher dosages and longer durations of therapy. In a study of 2,361 patients on HCQ for at least 5 years, the prevalence of retinal toxicity was less than 2 percent during the first 10 years of therapy in patients treated with 4.0 to 5.0 mg/kg of real body weight [54]. The current 2016 revised recommendations of the American Academy of Ophthalmology recommend that all patients undergo a baseline eye examination before or within a year of beginning the treatment with HCQ [55]. Given that that the likelihood of HCQ-induced retinopathy is rare with shortterm use (i.e. 4 months in this pilot study), no baseline ophthalmological evaluation will be mandated. However, patients with preexisting retinopathy will be disqualified from enrollment.

Table 1: Inclusion/Exclusion Criteria

Inclusion criteria for TPAIT [1, 56]	Exclusion criteria for TPAIT [1, 56]	
--------------------------------------	--------------------------------------	--

Inclusion criteria for HCQ phase	Exclusion criteria for HCQ phase		
Acceptance for TPAIT at CC Age range 18-65	Manufacturer's product label-contraindicated use of HCQ History of retinopathy Actual weight at enrollment <40 Kg Inclusion/exclusion criteria for TPAIT unmet		

4. Research Procedures

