4.1 Total pancreatectomy and islet isolation and transplantation

Pylorus-preserving TP with duodenectomy will be performed in all cases usually associated with splenectomy to preserve perfusion to body and tail. Warm ischemia time will be minimized. Finally, the pancreas and duodenum will be removed intact and flushed/drained via the splenic artery and vein respectively with UW solution [56]. Islet isolation and purification will be performed as described [56-58]. The islet Isolation Laboratory located at the Institute of Cellular Therapeutics at Allegheny General Hospital (AGH) has performed more than 60 islet isolating procedures for the Cleveland Clinic and will perform all of the islet isolation for the study [58]. The number of islets will be quantified as islet equivalents (IEQ). The isolated islet through standard method will be transported back to the Cleveland Clinic and transplanted as previously described [56].

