4.3 Blinding

The study will be single-blinded. The PI, biostatistician who will analyze the data, consultants, and technicians running assays will be blinded to the study arm into which the subjects have been randomized. An alphanumeric identifier that refers to the study subject without any indicators of study arm allocation will be used. Only the surgeons and the research coordinator, but not the personnel conducting the metabolic studies, will be un-blinded as to the study arm randomization.

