An outline of our budget is found in table 4. Data collection and entry will be performed by the study's investigators at no cost. MMTT testing at 6 and 12 months post-TPAIT is part of the standard-of-care testing in all centers performing TPAIT and thus no additional resources will be allocated for MMTT conduction. The cost of the RNA genomic analysis will be covered by the [name] Laboratory at Stanford University School of Medicine at no additional cost to us.

An application will be submitted for the Research Program Committee (RPC) Grant to cover half of the study expenses (around \$11,000). The planned date of submission of the application is February 6th, 2017. The remainder of the budget will be covered internally from EMI funding and the study's PI.

Item	Units	Estimated expense of items	Total
	needed		expenses
HCQ (4 month supply) and Placebo (4 month supply)	600 HCQ pills, 600 matching placebo	 \$1,200 for capsule manufacturing \$1,750 onetime pharmacy initiation fee \$60 monthly drug storage and inventory maintenance fee 	\$1,200 \$1,750 \$240 \$1,600 \$2,452
		 \$40 dispensing fee per occasion \$2,452 for generic HCQ (#600) 	

Table 4: Preliminary proposed budget

Seahorse XF24 Islet Capture	2	\$369	\$738
Microplates from Agilent Technologies			
Islet controls from Lonza	11	\$945	\$10,395
Pharma&Biotech			
Genomic Analysis		\$0 (to be covered by [name]'s Lab)	\$0
MMTT testing		\$0 (to be covered by insurance	\$0
		providers)	
Expense of islet transport and care from		\$0 (to be covered by [name]'s Lab,	\$0
CCF to AGH, from AGH to both		AGH, and insurance providers)	
Stanford and CCF			
Statistical support		~\$2,000	~\$2,000
Data collection and entry		\$0 (to be performed by study	\$0
		investigators)	
			~\$20,375

9. Extramural Grant Application Plan

An application will be submitted for the Research Program Committee (RPC) Grant to cover the

remainder cost of the study. The planned date of submission of the application is February 6th, 2017.

10. References:

- 1. Johnston, P.C., et al., Factors associated with islet yield and insulin independence after total pancreatectomy and islet cell autotransplantation in patients with chronic pancreatitis utilizing off-site islet isolation: Cleveland Clinic experience. J Clin Endocrinol Metab, 2015. **100**(5): p. 1765-70.
- 2. Sutherland, D.E., et al., *Total pancreatectomy and islet autotransplantation for chronic pancreatitis*. J Am Coll Surg, 2012. **214**(4): p. 409-24; discussion 424-6.

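### Section 4.3 un-blinds the surgeons without a stated reason, so knowledge of the arm could affect organ handling in a way that later masking cannot remove

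*Combined protocol and SAP*

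**What the plan says.** Section 4.3 (Blinding) divides the study staff into two groups. On the masked side: "The PI, biostatistician who will analyze the data, consultants, and technicians running assays will be blinded to the study arm". On the other side: "Only the surgeons and the research coordinator, but not the personnel conducting the metabolic studies, will be un-blinded as to the study arm randomization". The section gives no reason why surgeons need the allocation.

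Other sections bear on what that knowledge could do:

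- **Timing.** Section 4.2 places randomization before the pancreatectomy. Sections 3.2 and 4.4 start study drug or placebo 30 days before it.
- **Operative steps.** Section 4.1 covers the resection, the flush with UW solution and ischemia control, the last only as "Warm ischemia time will be minimized". It gives no numeric limit. It also assigns all islet isolation to an off-site laboratory.
- **Entry.** Section 3.2 has candidates "confirmed by a multidisciplinary team, consisting of a hepatobiliary surgeon, gastroenterologist, endocrinologist" and five further roles. Table 1 lists "Acceptance for TPAIT at CC" as a trial inclusion criterion.
- **Allocation.** Section 3.1: "Subjects from each group will be evenly distributed and randomized into the two treatment arms". Section 3.2 fixes 5 per arm. No sequence method, block size or concealment procedure is described.
- **Endpoint.** Section 5.1.1 defines the primary endpoint as the 90-minute C-peptide/glucose quotient divided by IEQ/Kg.
- **Supplies.** Table 4 in Section 8 budgets "600 HCQ pills, 600 matching placebo", together with pharmacy initiation and dispensing fees.

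**The concern.** Masking protects a trial only at the stages where the masked people act. Section 4.3 protects the metabolic testing, the assays and the analysis. It leaves the operation unprotected, and in this trial the graft is obtained at the operation. If the arms are handled differently in theatre, even unintentionally, the difference is already in the islets when the masked staff first measure anything. The analyst could not tell it from a drug effect.

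The same un-blinded role is represented on the team that confirms candidates. Anyone who knows earlier assignments in a small, exactly balanced trial has some ability to anticipate the next one.

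At stake is how a between-arm difference can be interpreted in a 10-patient comparison that is meant to inform a later trial.

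**Working it through.** **1. Can the surgeon know the arm when operating?** Yes. Allocation and the start of study drug precede surgery by about 30 days (Sections 3.2, 4.2, 4.4), and Section 4.3 un-blinds the surgeons.

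**2. Do surgeons influence the graft?** In part. Section 4.1 is in the passive voice, but resection, warm-ischemia control and flush are operative steps that come before the organ reaches the laboratory. Digestion, purification and counting come after and are done off-site. Section 4.3 does not name that laboratory as masked or un-masked.

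**3. What reaches the primary quotient?** Use the Section 5.5 planning values, CP/G 0.35 and IEQ/Kg 4500, and let the quotient be (CP/G) ÷ (IEQ/Kg).

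| Change | Quotient | Effect |
|---|---|---|
| None | 0.35/4500 = 7.78×10⁻⁵ | – |
| Mass and CP/G both +10% | 0.385/4950 = 7.78×10⁻⁵ | 0 |
| CP/G +10%, count unchanged (islet quality) | 0.385/4500 = 8.56×10⁻⁵ | +10% |
| Count +10%, CP/G unchanged | 0.35/4950 = 7.07×10⁻⁵ | −9% |

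Only non-proportional changes move the endpoint, and they can move it either way.

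**4. How much would such a shift matter?** First, the plan's own figure. With difference 0.12, SD 0.07, 5 per arm and one-sided α 0.05, the standard error is 0.07×√(2/5) = 0.0443. The noncentrality is 0.12/0.0443 = 2.71 on 8 degrees of freedom, with critical t 1.86, so power is 79.6%. Five is the smallest n that reaches 75%, which agrees with Table 3. Masking the surgeons leaves this unchanged.

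Now set the drug effect to zero and apply an assumed handling shift, expressed on the CP/G scale. The shift sizes are not in the documents.

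| Assumed shift | CP/G units | Noncentrality | One-sided type I error |
|---|---|---|---|
| 0 | 0 | 0 | 5% |
| 5% | 0.0175 | 0.40 | about 10% |
| 10% | 0.035 | 0.79 | about 18% |
| 20% | 0.07 | 1.58 | about 42% |

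**5. How predictable is the next assignment?** Take an observer who knows all past arms and always guesses the under-filled one. In a balanced sequence of 2n, the expected number of correct guesses is n + ½(4ⁿ/C(2n,n) − 1).

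- Fixed 5:5, n = 5: 5 + ½(1024/252 − 1) = 6.53 of 10. The expected number certain in advance is 2n/(n+1) = 10/6 = 1.7.
- Assumed yield groups of 6 and 4, each split evenly: 4.10 + 2.83 = 6.93.
- Assumed pairs: 5 × 1.5 = 7.5.
- Without that knowledge: 5.

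Only the first figure rests on the stated 5:5 split alone. The next two depend on group or block sizes that the documents do not give.

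**6. Is there room to act on a guess?** Little. Section 3.3 expects 10–13 TPAIT cases in 12 months, and Section 3.4 expects to fill 10 places in the same period. That leaves 0 to 3 spare candidates before any refusals or exclusions.

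**The case against.** The strongest reply is that the endpoint was built to absorb differences in islet mass. A reader might infer that an un-blinded surgeon biases the primary comparison directly, because IEQ infused is its divisor. The documents do not support that. Proportional changes cancel, and a surgeon who raised yield in the HCQ arm without a matching rise in C-peptide/glucose would work against HCQ. Surgeons also do not set the graft alone, since isolation is off-site. Section 4.1 describes one technique for all patients, and nothing suggests that it would vary by arm. All of this stands, and it limits the concern to islet quality and other non-proportional effects.

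A reader might also infer that surgeons steer who enters. The documents support this only weakly. The team's surgeon is one of eight listed roles and is not stated to be the operating surgeon. A nurse coordinator takes consent (Section 7), and nearly every candidate must be enrolled. The guessing figures show predictability, not that anyone acts on it.

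Nor do the documents assign surgeons a part in inpatient care, so post-operative management cannot be counted as a further route.

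Finally, un-blinding might serve safety: study drug continues perioperatively, and Section 4.7 anticipates possible hypoglycemia. That is plausible but not stated, and emergency un-blinding would meet it. The endpoint is a laboratory value with masked testing, which protects measurement but not what happened to the organ beforehand.

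**Conclusion.** The concern holds as an avoidable and unexplained gap in masking. Surgeons may know the arm while performing steps that could affect islet quality, and none of the masking in Section 4.3 acts early enough to remove the result. The risk is a possible, non-proportional effect on the primary quotient, and its direction is unknown.

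The documents allow no estimate of its size. The type I error figures show how little imbalance 5 per arm tolerates if the shift were 5% to 20%; they do not predict that it will occur. They assume that the CP/G SD of 0.07 applies to the comparison, with equal variances and no drug effect.

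Selection is a secondary and weaker route, with 6.5 rather than 5 correct guesses in 10 under a fixed 5:5 split. Two links are inferred from role and not stated: that surgeons perform the steps in Section 4.1, and that the team's surgeon may be among those un-blinded. The change should be made because it is cheap and no benefit of un-blinding is given.

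**What to change.** Revise Section 4.3 so that:

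- surgeons and all other members of the multidisciplinary selection team are masked in the same way as the PI until the last participant's 12-month MMTT is complete;
- the dispensing pharmacy holds the allocation list and logs every emergency un-blinding;
- the text states whether the research coordinator stays un-blinded and, if so, keeps that role out of eligibility decisions.

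If there is a reason to leave surgeons un-blinded, state it, describe a concealed sequence, and have each candidate's eligibility recorded before allocation. While the text is open, reconcile Section 3.1, which calls the trial both open label and single-blinded with placebo control.

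**Cost.** A short revision of Section 4.3 and a pharmacy instruction. No participants are added and power is unchanged. Matching placebo is already in Table 4, with a \$1,750 pharmacy initiation fee and \$1,600 for dispensing at \$40 per occasion (1600/40 = 40 occasions, or 4 for each of 10 participants). The downside is a short delay when a surgeon needs emergency un-blinding.

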4.4 HCQ administration

Arm 1 (n=5): Subjects will receive a pre-transplant HCQ 200 mg daily dose 30 days prior TPAIT followed by HCQ use for an additional 3 months post-surgery. Oral medications are continued perioperatively. Patients are typically ordered for "NPO except for medications" starting from post-operative day 1 which will not preclude the administration of HCQ in the peri-transplant period.

Arm 2 (n=5) subjects will receive placebo treatment following the same schedule as in Arm 1.

4.5 Exploratory mechanistic studies

All subjects will undergo a MMTT to assess islet cell function at 6 and 12 months following TPAIT (in addition to MMTT pre-surgery performed as standard of care, and whose results will be used for prerandomization in this pilot). Baseline metabolic tests obtained too early after surgery may not be indicative of islet function, due to insulin supporting therapy administered for several weeks after transplantation. Also, compelling data indicate that stabilization of islet function may require up to 1 year to occur. Blood glucose and C-peptide serum levels will be measured in peripheral blood samples immediately prior and subsequent to MMTT. Laboratory tests will be measured in CCF hospital laboratory.

The research coordinator will contact the subjects at 3, 6 and 12 months for interview on the course of follow up and will assist in scheduling the 6 and 12-month appointments for MMTT.

4.6 Innovation:

4.6.1 Part I: Mitochondrial Function and Metabolic Outcomes in TPAIT

Small amounts of digest left after islet isolation, that would normally be discarded, will be used for this study. The islets from the digest will be collected and will undergo extracellular efflux analysis through the Seahorse XF analyzer located in the [name] Laboratory of the Cleveland Clinic Lerner Research Institute for mitochondrial function assessment. Commercially available normal human islet cells for experiments will be used as control. Controls will be shipped within 1 week of planned TPAIT date and will be compared simultaneously with islets isolated from study subjects. A protocol developed by Seahorse Bioscience in collaboration with the Mitochondrial Advancing Research through Collaborations

at Boston University School of Medicine will be used for the Seahorse XF analyzer islet analysis [59]. The OCR of isolated islets will be analyzed with metabolic outcomes from post-transplantation follow-up.

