Islet cell survival and function, both short- and long-term are governed by the degree of cellular damage: both pre-existing from the underlying inflammation seen in chronic pancreatitis, and inflicted damage by the isolation and transplantation processes. Reports on beta cell mass among CP patients estimate 29% loss of the fractional beta cell area as a result of chronic inflammation and fibrosis, coupled with an additional 21% reduction in overall pancreatic mass resulting in more pronounced deficit in total islet mass [11]. As for inflicted damage, the islet isolation procedure is a key pre-transplant factor in islet mass loss [12, 13]. Harmful events also occur in the early post-AIT period and are induced by stressors such as hypoxia, hyperglycemia, and the infiltrating innate immune cell-derived cytokines and other pro-inflammatory factors [5, 14, 15]. A pro-coagulatory and pro-inflammatory cascade is activated within minutes after islet infusion back into the host and actively accelerate the injury to transplanted islets [16]. The levels of inflammatory cytokines such as IL-1Ra, IL-6, IL-8 and IL-10 have been reported to peak within the first 6 hours of islet infusion and gradually subside to pre-transplant levels days from islet transplantation [5, 16].

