[name] and her clinical staff will monitor the subjects for HCQ-emergent adverse events prior to discharge and the research coordinator will follow-up by phone contact throughout the duration of the trial.

Table 2: Study Timeline

	T= -1 months	T=0 (TPAIT day)	T = +3 months	T = +6 months	T = +12 months
HCQ group (n=5)	- MMTT #1 - Start of HCQ	- Seahorse XF analyzer for isolated islets ([name] Lab) - Genomic analysis ([name] Lab)	- Discontinue HCQ	- MMTT #2	- MMTT #3
Placebo group (n=5)	- MMTT #1 - Start of placebo	- Seahorse XF analyzer for isolated islets ([name] Lab) - Genomic analysis ([name] Lab)	- Discontinue placebo	- MMTT #2	- MMTT #3

Figure 1: Study Timeline

5. Data Analysis

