5.1.3.2 Part II: Genome-wide Gene Expression in TPAIT Patients

Differential gene expression calls will be done on isolated islets. These will be compared to appropriate control gene expression sets [52].

5.2 Study outcomes:

5.2.1 Primary outcomes:

- Increased quotient of stimulated C-peptide/glucose level normalized for IEQ/Kg infused in response to MMTT at 12 months in the HCQ-treated compared to placebo arm.

5.2.2 Secondary outcomes:

- Higher C-peptide AUC in response to MMTT 12 months in the HCQ-treated compared to placebo arm.
- Higher ratio of C-peptide AUC to glucose AUC in response to MMTT at 12 months in the HCQ-treated compared to placebo arm.

5.2.3 Innovative outcomes:

- Lower rates of oxygen consumption within isolated islets from CP patients compared to commercial controls
- Higher rates of oxygen consumption within isolated islets of HCQ-treated subjects compared to placebo.
- Full RNA sequence library for isolated islets from CP patients

5.3 Data collection:

The clinical data will be collected under auto islet registry stored in REDCap. All data in the Islet Isolation Laboratory at the Institute of Cellular Therapeutics, Allegheny Health Network and [name] Laboratory of the Cleveland Clinic Lerner Research Institute will be de-identified and collected into Microsoft Excel as medium, then transferred to REDCap by the investigators. All investigators will have received proper HIPPA training.

5.4 Data access and confidentiality:

All data will be collected either directly into REDCap or indirectly through Microsoft Excel on CCF Desktop computer as medium. The data will contain no personal health identifier (PHI) when it is being shared with investigators outside of the CCF. A study ID will be assigned to each subject. The deidentified clinical data will be shared for the purpose of manuscript construction under the standard user data agreement from the CCF IRB Committee. All investigators will have received proper HIPPA training.

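### The oxygen-consumption difference between CP islets and commercial islets cannot be attributed to chronic pancreatitis alone, because source, donor, handling and time since isolation all change with disease status

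*Combined protocol and SAP*

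**What the plan says.** **Subject tissue.** Section 4.6.1 takes its material from what remains after isolation: "Small amounts of digest left after islet isolation, that would normally be discarded, will be used for this study". It adds that the islets are collected from this digest before analysis. Section 4.1 places all isolations at one off-site laboratory, after which "The isolated islet through standard method will be transported back to the Cleveland Clinic and transplanted as previously described". Table 2 lists "Seahorse XF analyzer for isolated islets" in the T=0 column for both arms.

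**Control tissue.** Section 4.6.1: "Commercially available normal human islet cells for experiments will be used as control". On timing: "Controls will be shipped within 1 week of planned TPAIT date and will be compared simultaneously with islets isolated from study subjects". No isolation date, culture time or donor description is given for the controls. The budget (section 8, Table 4) has 11 control units for a trial of 10 subjects.

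**Use of the contrast.** Section 5.2.3 names as an innovative outcome "Lower rates of oxygen consumption within isolated islets from CP patients compared to commercial controls". Section 2.1.1 states the matching hypothesis of mitochondrial dysfunction in CP islets relative to normal ones. A separate outcome in 5.2.3, "Higher rates of oxygen consumption within isolated islets of HCQ-treated subjects compared to placebo", does not involve the controls.

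**Analysis.** Section 5.5 deals only with the C-peptide/glucose quotient. It gives no analysis for OCR.

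**The concern.** The scientific question is whether CP islets respire less than normal islets. To answer it, the two tissues should differ in disease and in little else that affects OCR. Here they also differ in who isolated them, how they travelled, how long they waited and which donors they came from. None of these is matched, recorded or adjusted for in the text. The shipping window is also tied to the planned surgery date, so the wait can change if surgery moves.

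The protocol's background section recognises that processing matters: "the islet isolation procedure is a key pre-transplant factor in islet mass loss". That statement is about islet mass and applies to both tissues, so it shows only that handling is not neutral. It does not show which tissue is worse off.

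At stake is the interpretation of one exploratory outcome. It is not a trivial part of the project: the control islets account for $10,395 of about $20,375, or 51% of the budget.

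**Working it through.** No figure in the plan bears on this point, so there is nothing to reproduce. The check is structural, followed by two illustrations whose inputs are assumptions.

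**1. What differs between the tissues**

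| Factor | CP islets | Control islets | Equalised by the plan? |
|---|---|---|---|
| Assay run | Same run | Same run | Yes (4.6.1) |
| Isolation site | One off-site laboratory (4.1) | Supplier's product; site not stated | No |
| Starting material | Islets collected from residual digest (4.6.1) | Commercial preparation (4.6.1) | No |
| Transport | Islets return to the centre (4.1) | Shipped within 1 week of planned surgery (4.6.1) | Both travel; not matched |
| Time since isolation | Not stated; Table 2 lists the assay at T=0 | Not stated | No, and not recorded |
| Donor | The subject | Not described | No |

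**2. What a within-run difference estimates**

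On the log scale, write OCR in a run as a run effect + disease effect δ (CP only) + source-and-donor effect σ (CP route v commercial route) + β × hours since isolation. Subtracting control from CP within a run gives

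δ + σ + β × (hours for CP − hours for control).

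The run effect cancels, which is the benefit of simultaneous assay. The other terms remain. Every CP sample has one source and every control has another, so δ and σ always appear together and no analysis can separate them. If hours were recorded and varied between runs, the time term could be explored, but removing it would still leave δ + σ.

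**3. Illustration: a real deficit hidden**

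Assumptions, none from the documents: the true CP deficit is 20%, only the controls lose OCR, and the loss is r per day for k days. The apparent deficit is 1 − 0.80/(1 − r)^k.

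| | r = 1% | r = 3% | r = 5% |
|---|---|---|---|
| k = 4 | 16.7% | 9.6% | 1.8% |
| k = 7 | 14.2% | 1.0% | −14.6% |

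For example, with r = 3% and k = 7: 0.97^7 = 0.808, and 1 − 0.80/0.808 = 1.0%. A negative value means that CP islets appear to respire more than controls.

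**4. Illustration: a deficit created**

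Assumptions: no disease effect, 10 CP and 10 control preparations treated as independent with equal variance, and a handling shift of b standard deviations (SD) towards lower CP OCR. The t statistic has 18 degrees of freedom and noncentrality b × √(10/2) = 2.236b. The chance of nominal significance at 0.05 is:

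| b (SD) | Two-sided | One-sided |
|---|---|---|
| 0 | 0.05 | 0.05 |
| 0.25 | 0.08 | 0.13 |
| 0.5 | 0.19 | 0.29 |
| 1.0 | 0.56 | 0.69 |

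The two illustrations point in opposite directions. The documents do not say which is nearer the truth.

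**5. Which outcomes are affected**

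HCQ versus placebo OCR compares two arms whose islets follow the same route and does not use the controls. The primary endpoint is an MMTT quotient measured in subjects. Neither depends on the commercial islets.

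**The case against.** The best defence has four parts.

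- **The controls are run alongside each subject.** True, and with 11 units for 10 subjects about one control per subject looks feasible. This deals with run effects only.
- **A cited assay protocol governs the laboratory work.** Section 4.6.1 says that a published islet protocol for the analyser will be used. It may fix loading, recovery and normalisation for both tissues. Its text is not in the documents, so a reader should not conclude that well loading or medium is uncontrolled. It could not, however, make the two tissues share a source, a donor or an isolation time.
- **Both tissues are isolated elsewhere and travel.** This stands and narrows the contrast between the routes, but it does not make them equal.
- **Section 5.2.3 is an openly worded expectation.** It names commercial controls as the comparator and attaches no test or decision rule. That stands too. The risk lies in how the result is read, since section 2.1.1 frames it as mitochondrial dysfunction in CP.

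A reader might also infer more than the documents support:

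- That controls are held for 7 days. The text gives a shipping window, does not say whether it falls before or after the planned date, and states no holding time.
- That subjects' islets are certainly assayed on transplant day. The T=0 column of Table 2 also lists the genomic analysis, for which section 4.6.2 has islets shipped to another institution, so T=0 may mean the day of collection.
- That raw digest with acinar tissue is loaded. Section 4.6.1 says islets are collected from the digest; their purity is not stated.

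**Conclusion.** The concern holds in a limited form. As planned, the difference between CP and commercial islets combines disease with source, donor, handling and time since isolation, and simultaneous assay does not undo this. The difference cannot be attributed to CP alone. This follows from the sampling scheme and needs no assumption about loss rates.

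The size and direction of the bias are unknown from the documents. It would be tempting to say that handling will reverse the CP deficit. Only the most extreme assumed combination above (5% a day for 7 days, with no loss in CP islets) does so, and both the loss rate and the 20% deficit are assumptions. It would be equally tempting to think that a shared recovery period would license a CP-deficit reading. It would not, because donor and supplier would still differ with disease status.

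Severity is minor: one exploratory outcome in a 10-subject pilot, with HCQ versus placebo OCR and the primary MMTT endpoint untouched.

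**What to change.** In section 4.6.1:

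- Tie shipment of control islets to the confirmed surgery date instead of the planned one.
- Record isolation-to-assay hours for every subject and control sample, with whatever donor data are available.
- State that the loading, recovery and normalisation steps of the cited assay protocol are applied identically to both tissues.

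In section 5.2.3:

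- Estimate CP versus control as within-run paired differences, and show them against the difference in isolation-to-assay time.
- Describe the result as islets from CP digest compared with shipped commercial islets. Report it as descriptive, not as evidence of a CP deficit.

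The cost is one recorded time per sample, less flexibility in ordering controls, and a weaker claim for one exploratory outcome. No patients or patient procedures are added.
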